Participants who have already completed the 9 month study will receive an updated copy of the consent and assent form via mail with a request to sign the updated consent and assent forms. See Appendix III for a copy of a letter to be included with the updated consent and assent. Once the updated consent and assent are received by the investigators at Norton Children's Gynecology the post survey follow up will be sent to the participant by SMS text message via Qualtrics. Study participants who are seen in the office for their 9 month follow up visit will be re-consented in the office.

Patients diagnosed with a sexually transmitted infection during the course of the study will be removed from the study and their data will be excluded from analysis.

All completed demographic data collection forms and electronic menstrual calendars will be kept in a database, de-identified, and stored on a password-protected computer. Study size will be a convenience sample. Based on the current rate of etonogestrel implant insertions in our practice, it is anticipated that 30 participants can be recruited over a six-month period of time.

Data Collection and Analysis

All patients who meet the inclusion criteria and enroll in the study will be sent a text message daily for 90 days (3 months). The daily message will prompt the participant to indicate the bleeding level for the day. This single question will have 4 options:

1. Bleeding Day
2. Spotting Day
3. Bleeding Free Day
4. Prefer not to answer today.

On day 90, descriptive tallies of the responses will be done. Using SPSS v20, an algorithm will count the number of bleeding days, spotting days, and bleeding free days and prefer not to answer (PNA) days; the data record for each participant will contain four count variables (bleeding, spotting, free, PNA). Secondly, the algorithm will identify and tally –according to WHO guidelines in Table 1 - bleeding-spotting episodes (BSE), amenorrhea (AM), infrequent bleeding (IF), normal frequency of bleeding (NF), frequent bleeding (FB), and prolonged bleeding (PB).

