Participants who have at least a single episode of FB or PB will be assigned the label of “bothersome bleeding”. Those without a single episode of FB or PB will be labeled “normal bleeding”. Participants in the Bothersome Bleeding group will be offered aygestin to control the bothersome bleeding. Participants in the Normal Bleeding group will continue as before, with no additional medications. Following the principle of intent-to-treat, data from those in the Bothersome Bleeding group will be assigned to the aygestin group, despite that they are not taking it.

During the first month, participants in the Bothersome Bleeding group will take one 5 mg tablets of aygestin twice daily (morning and evening). After 30 days, the dose of aygestin will be halved, such that only one 5 mg tablet is taken daily. Sixty days

later, the Bothersome Bleeding group will discontinue aygestin. Ninety days later, both the normal group and the Bothersome Bleeding group will be re-evaluated.

Data Analysis

A descriptive table will be used to sort participants into Normal Bleeding and Bothersome Bleeding. Non-parametric and parametric statistics will be used to compare the demographics of these two groups.

A **dose-response curve** covering six months will be plotted for the Bothersome Bleeding group to visually reveal the impact of one month of 10 mg of aygestin vs. two months of 5 mg aygestin vs. three months 0 mg of aygestin. Plotted on the curve will be the group averages of the daily bleeding value (1 for no bleeding, .5 for spotting, 0 for bleeding). A second **no-dose curve** will be added to the X-Y plot for the six months of data from the Normal Bleeding group.

Repeated Measure Multivariate Analysis of Variance (RM-ANOVA) with a Between-Subjects variable included, will be conducted (assuming sufficient data is available – e.g., low PNA rates) to compare the first 30 day average bleeding value, the 90 day bleeding average, and the 180 day bleeding average between the two groups.

Planned post-hoc comparisons will evaluate changes between the control group and intervention group at the three time points.

Additional analyses may also include regression analysis to assess for predictive factors related to response to aygestin.

TIMELINE:

October 2014	IRB Submission
November 2014	Anticipated IRB Approval
November 2014 – July 2015	Data Collection
August – September 2015	Data Analysis

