Use of Norethindrone Acetate for Management of Bleeding Associated With the Etonogestrel Contraceptive Implant

NCT02353247

Nov. 14, 2016

Data Analysis Plan

The primary hypothesis was analyzed using repeated measures ANOVA (RM-ANOVA) with two groups and three measurements (summary statistics at day-90, day-180, and day-270). To have at least 80% *a-priori* power to detect a medium effect size ($f = 0.25$) at $\alpha = 0.05$, a total sample size of 28 was required with approximately equal sized groups. (G*Power version 3.1.9.2¹; Faul, Erdfelder, Lang, & Bucher, 2007). Anticipating and reacting to high attrition rates, 72 participants were enrolled.

Data cleaning and management was done to identify participants who responded to daily SMS surveys at least 189 times (70% of the 9-month trial). Fifteen (21%) of the 72 participants provided fewer than 100 responses. Another 14 participants (19%) provided between 100 and 188 responses. An additional four participants (9.7%) were removed because they did not respond at least 70% of the days during each 90-day time period. The final data set consisted of 39 participants: 18 in the No Intervention arm and 21 in the Intervention arm. Post-hoc analysis indicated the study was powered at 93%.

¹ NOTE: Faul, F., Erdfelder, E., Lang, A.-G., & Buchner, A. (2007). G*Power 3: A flexible statistical power analysis program for the social, behavioral, and biomedical sciences. *Behavior Research Methods*, 39, 175-191.

Data collection was done with Qualtrics™ (Provo, Utah) and analyses were done using Microsoft Excel (Redmond, Washington) and IBM SPSS Statistics for Macintosh (version 24, Chicago, Illinois).

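### The SAP reports the repeated measures ANOVA at day 90, 180 and 270 where the protocol planned 30-, 90- and 180-day averages, without explanation; its first time point is probably the window that sorted the groups

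*Protocol*

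**What the plan says.** **Planned test.** Under Data Analysis, the protocol will use a repeated measures ANOVA with a between-subjects factor "to compare the first 30 day average bleeding value, the 90 day bleeding average, and the 180 day bleeding average between the two groups". The daily value is 1 for no bleeding, 0.5 for spotting and 0 for bleeding. The protocol does not say whether the days count from insertion or from the start of treatment.

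**Reported test.** The SAP's Data Analysis Plan, dated Nov. 14, 2016 and in the past tense, gives two groups and three measurements: "summary statistics at day-90, day-180, and day-270". It does not name the statistic, say which ANOVA effect is primary, or mention a change from the protocol. It already gives the exclusions and the analysed numbers: "The final data set consisted of 39 participants: 18 in the No Intervention arm and 21 in the Intervention arm".

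**How the groups arise.** They are not randomised. Under Data Collection and Analysis, "On day 90, descriptive tallies of the responses will be done", and "Participants who have at least a single episode of FB or PB will be assigned the label of" bothersome bleeding, where FB and PB are the frequent and prolonged bleeding of Table I. That group is offered the study drug; the others are the controls.

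**The concern.** Two things are at stake.

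- **Prespecification.** The test of the primary hypothesis differs from the one in the protocol, in a document written with the data in hand. A reader cannot tell whether these time points were fixed for this test in advance.
- **Validity.** Participants sorted on how they bled in days 1-90 tend to drift back toward their usual level afterwards. The bothersome group looks better and the control group worse, with no drug involved. If days 1-90 enter as the first repeated measure, that convergence is itself a group-by-time interaction and can be read as a drug effect.

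**Working it through.** **1. Do the two sets of time points agree under any origin?**

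| Protocol counted from | Protocol's 30/90/180 in study days | Difference from SAP's 90/180/270 |
|---|---|---|
| Treatment start (taken as day 91) | averages ending at days 120, 180, 270 | The 30-day on-treatment average gives way to a pre-treatment value. If the averages are cumulative, the third measure also changes (days 91-270 against 181-270). |
| Insertion | averages ending at days 30, 90, 180 | The 30-day average is dropped and day 270 is added. |

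The six-month curve planned in the same protocol section favours the first origin but does not settle it. Neither origin reconciles the documents.

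**2. Which test do the SAP's power figures fit?** From the SAP: f = 0.25, alpha 0.05, 2 groups, m = 3 measurements; "a total sample size of 28 was required with approximately equal sized groups"; and "Post-hoc analysis indicated the study was powered at 93" per cent. The correlation r between measurements is not given.

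For a within-subject or group-by-time F test under sphericity, lambda = f² × N × m / (1 − r), with 2 and 2(N − 2) degrees of freedom. At r = 0.5:

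- N = 28: lambda = 0.0625 × 28 × 3 / 0.5 = 10.5, power 0.812 (N = 26 gives 0.778).
- N = 39: lambda = 0.0625 × 39 × 3 / 0.5 = 14.6, power 0.929.

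Both SAP figures reproduce, and together only for r of about 0.49-0.51. A between-group main effect at r = 0.5 would need 86 participants. So the figures fit a within-subject or group-by-time test, not a between-group test. They depend on the number of measurements, not on which days are used, so they do not support either set of days.

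**3. Is day 90 the sorting window?** The SAP removed four participants because "they did not respond at least 70% of the days during each 90-day time period". That suggests three 90-day periods, the first being days 1-90. It is an inference.

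**4. Size of the effect if it is.** The assumptions are: no drug effect, 21 against 18, normal 90-day means with correlation r, and the worst 21 of 39 labelled bothersome on a score correlated q with window 1. If the label is the window-1 value itself (q = 1), the average gap is 1.56 SD in window 1 and r × 1.56 later, so 0.5 × 1.56 = 0.78 SD at r = 0.5. Rejection rates of the nominal 5% group-by-time test with all three windows and equal correlation (10,000 runs per cell) were:

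| r | q = 0.6 | q = 0.8 | q = 1.0 |
|---|---|---|---|
| 0.3 | 43% | 72% | 94% |
| 0.5 | 30% | 53% | 78% |
| 0.7 | 19% | 32% | 50% |
| 0.8 | 14% | 23% | 34% |

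Repeat runs differ by a point or two (up to 79% at r = 0.5 and 36% at r = 0.8). At r = 0.9 the range is 9-19%. With windows 2 and 3 only, the rate is about 5% under equal correlation and roughly 7-26% if correlation decays as r squared. That is below the three-window rate in every cell.

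**5. Daily diaries labelled by Table I's rule.** In six assumed settings (r from 0.30 to 0.82) with no drug effect, the SAP windows rejected in 27-75% of runs, the protocol averages from insertion in 22-57%, and the protocol averages from day 91 in 4-5%. That last figure assumes stable bleeding tendencies. Letting them drift between windows (autocorrelation 0.7, four of the settings) raised it to 6-13%, against 52-82% for the SAP windows.

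**The case against.** A reader might infer that the time points were chosen after seeing results. The documents do not support that. Days 90, 180 and 270 match the protocol's 3-, 6- and 9-month visits and its 90-day response cycles, so an ordinary explanation exists. What stands is that nothing shows these times were prespecified for this test.

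A reader might also take the outcome to have been switched. The SAP's statistic is unnamed; it may well be the protocol's average bleeding value.

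The strongest statistical objections are these:

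- **The test is inferred.** The SAP does not name its primary effect, and its power figures fit a within-subject test as well as group-by-time. The false-positive rates apply only to group-by-time.
- **r may be high.** The r of 0.5 is a planning value. The protocol's Background calls bleeding in the first three months predictive of later bleeding, which favours a higher r and a smaller problem. At r = 0.9 the rate is still 9-19%.
- **A baseline is legitimate.** It is, in general. The difficulty is a baseline that defined the groups.
- **The protocol already plans post-hoc comparisons** between groups at its three time points. If these cover day 180 against day 270, that contrast avoids the sorting window. The limit therefore falls on the overall interaction, not on every comparison.

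**Conclusion.** The unexplained difference between the documents is established under either time origin, as is the fact that the SAP was written after the data set was final. The regression-to-the-mean problem is conditional. It requires that day 90 summarises days 1-90 and that the group-by-time effect carries the conclusion; both are likely and neither is stated. On those conditions, with equal correlation and q of 0.6-1.0, the illustrative false-positive rate is about 30-79% at r = 0.5, 14-36% at r = 0.8 and 9-19% at r = 0.9.

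It would be tempting to conclude that the protocol's own version was sound. Counted from insertion it shares the defect. Counted from treatment start it reduces the problem, but does not always remove it if correlation falls with lag. The missing origin therefore matters. The point should be acted on because it concerns the test of the primary hypothesis.

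**What to change.** 1. State one time origin in both documents. Day 91 must be reconciled with the protocol's follow-up, which is timed from medication initiation in one place and from insertion in another. Name the outcome as the mean daily bleeding value (1/0.5/0), and say which ANOVA effect is primary.
2. Label the day 90/180/270 analysis as specified after data collection. State that its overall group-by-time test cannot separate a drug effect from regression to the mean.
3. Treat days 1-90 as the selection period and report them descriptively. Base the tested between-group change on post-labelling data, at minimum day 180 against day 270. Label this contrast post hoc too, and note that some regression to the mean may remain. Finer windows following the scheduled treatment phases are optional.

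**Cost.** Wording, plus re-summarising daily data already held. The before/after contrast becomes descriptive, and the groups remain non-randomised. Power is limited: for an assumed effect of 0.5 SD on days 91-180 that vanishes on days 181-270, the two-window contrast has about 33% power at r = 0.5 and 50% at r = 0.7.

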APPENDIX I:

DEMOGRAPHIC DATA COLLECTION FORM:

What is your age?

_____ Years old

Are you Hispanic or Latino?

_____ Yes, Hispanic or Latino

_____ No, not Hispanic or Latino

How would you describe yourself?

Choose one or more from the following

ethnic/racial groups:

_____ American Indian or Alaskan Native

_____ Asian

_____ Black or African American

_____ Native Hawaiian or Pacific Islander

_____ White

What is your zip code?

Health insurance provider

_____ Private insurance

_____ Medicaid (i.e. passport)

_____ No insurance

Sexual partners

_____ In the past month

_____ In your lifetime

Use of prior contraceptive methods

_____ Pills

_____ Patch

_____ Ring

_____ Depo-Provera

_____ Intrauterine device

_____ Condoms

_____ Spermicide

_____ Sponge

_____ Diaphragm

_____ Withdrawal

Are you currently using condoms?

_____ Most / All of the time

_____ Some of the time

_____ None of the time

Have you ever had a sexually transmitted infection?

_____ Chlamydia

_____ Gonorrhea

_____ Trichomonas

_____ Herpes

_____ HIV / AIDS

_____ Hepatitis B

_____ Hepatitis C

_____ Syphilis

How old were you when you started having periods?

_____ Years old

Are you currently having a monthly menstrual cycle?

_____ Yes

_____ No

What was the first day of your last menstrual period?

What is your weight?

_____ Pounds

What is your height?

_____ Inches

When was your implant put in?

_____ Date

Appendix II:

1	How do you feel about using text messages as a way of telling the researchers about your period or break-through bleeding?	Very happy	Happy	Neutral	Un-happy	Very Un-happy
2	Did you answer the text messages every day?	All of the time	Most of the time	Some of the time	Hardly ever	Never [1]
3	When you were not able to answer the text message, what were the reasons for not doing so? Choose all that apply	Busy doing some-thing else	Forgot about to answer	Lost access to my phone	Ran out of minutes/ texts	Other
4	Did you ever feel annoyed or unhappy about receiving texts from the researchers?	No, never	Rarely	Sometimes	About once a week	Every day
5	Would you be more or less likely to enroll in a future study if that study also used text messages to collect your information?	Much less likely to enroll	Less likely to enroll	Makes No difference	More likely to enroll	Much more likely to enroll
6	Text messages were sent at 6pm every evening. How did you feel about the timing of the texts?		Better earlier in the day	The timing was fine	Better later in the day	
7	For this type of research, another way of collecting data is to have you write your information into a paper-based diary each day. Which method of data collection would you prefer?	Strongly prefer paper-based diary	Prefer paper based diary	Either would be fine	Prefer text-based	Strongly prefer text-based
8	Throughout the study period (up to 270 days), how often did you change your cell phone plan (for example, get a new phone number, change your plan to get more or fewer messages, etc.)?	Never	1 time	2 times	3 times	More than 3 times
9	Did the text message format make it easier or harder for you to give your answer truthfully?	Much Easier	Easier	No difference	Harder	Much Harder
10	How likely do you think your friends would be willing to enroll in a study that uses text messaging for collecting data?	Very likely	Likely	Neither likely nor unlikely	Unlikely	Very unlikely
11	Do you plan to keep your Nexplanon for the next 9 months or longer?	Already removed it	No	Un-decided	Yes	
12	Would you recommend Nexplanon to a friend?	Definitely no	Maybe no	Undecided	Maybe yes	Definitely yes

Appendix II:

1	How do you feel about using text messages as a way of telling the researchers about your period or break-through bleeding?	Very happy	Happy	Neutral	Un-happy	Very Un-happy
2	Did you answer the text messages every day?	All of the time	Most of the time	Some of the time	Hardly ever	Never
3	When you were not able to answer the text message, what were the reasons for not doing so? Choose all that apply	Busy doing some-thing else	Forgot about to answer	Lost access to my phone	Ran out of minutes/ texts	Other
4	Did you ever feel annoyed or unhappy about receiving texts from the researchers?	No, never	Rarely	Sometimes	About once a week	Every day
5	Would you be more or less likely to enroll in a future study if that study also used text messages to collect your information?	Much less likely to enroll	Less likely to enroll	Makes No difference	More likely to enroll	Much more likely to enroll
6	Text messages were sent at 6pm every evening. How did you feel about the timing of the texts?		Better earlier in the day	The timing was fine	Better later in the day	
7	For this type of research, another way of collecting data is to have you write your information into a paper-based diary each day. Which method of data collection would you prefer?	Strongly prefer paper-based diary	Prefer paper based diary	Either would be fine	Prefer text-based	Strongly prefer text-based
8	Throughout the study period (up to 270 days), how often did you change your cell phone plan (for example, get a new phone number, change your plan to get more or fewer messages, etc.)?	Never	1 time	2 times	3 times	More than 3 times
9	Did the text message format make it easier or harder for you to give your answer truthfully?	Much Easier	Easier	No difference	Harder	Much Harder
10	How likely do you think your friends would be willing to enroll in a study that uses text messaging for collecting data?	Very likely	Likely	Neither likely nor unlikely	Unlikely	Very unlikely
11	Do you plan to keep your Nexplanon for the next 9 months or longer?	Already removed it	No	Un-decided	Yes	
12	Would you recommend Nexplanon to a friend?	Definitely no	Maybe no	Undecided	Maybe yes	Definitely yes

Use of Norethindrone Acetate for Management of Bleeding Associated With the Etonogestrel Contraceptive Implant

NCT02353247

Nov. 14, 2016

Data Analysis Plan

The primary hypothesis was analyzed using repeated measures ANOVA (RM-ANOVA) with two groups and three measurements (summary statistics at day-90, day-180, and day-270). To have at least 80% *a-priori* power to detect a medium effect size ($f = 0.25$) at $\alpha = 0.05$, a total sample size of 28 was required with approximately equal sized groups. (G*Power version 3.1.9.2¹; Faul, Erdfelder, Lang, & Bucher, 2007). Anticipating and reacting to high attrition rates, 72 participants were enrolled.

Data cleaning and management was done to identify participants who responded to daily SMS surveys at least 189 times (70% of the 9-month trial). Fifteen (21%) of the 72 participants provided fewer than 100 responses. Another 14 participants (19%) provided between 100 and 188 responses. An additional four participants (9.7%) were removed because they did not respond at least 70% of the days during each 90-day time period. The final data set consisted of 39 participants: 18 in the No Intervention arm and 21 in the Intervention arm. Post-hoc analysis indicated the study was powered at 93%.

¹ NOTE: Faul, F., Erdfelder, E., Lang, A.-G., & Buchner, A. (2007). G*Power 3: A flexible statistical power analysis program for the social, behavioral, and biomedical sciences. *Behavior Research Methods*, 39, 175-191.

Data collection was done with Qualtrics™ (Provo, Utah) and analyses were done using Microsoft Excel (Redmond, Washington) and IBM SPSS Statistics for Macintosh (version 24, Chicago, Illinois).

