cervical mucus inhibiting sperm penetration into the uterus, and alteration of the endometrium. In the clinical trial of 301 Nexplanon (the radiopaque etonogestrel implant) users, no woman became pregnant while the implant was in situ, up to and including 14 days after implant removal. This resulted in an estimated overall Pearl Index of 0.0 (95% CI, 0.0 – 0.56) (12); which translates clinically to >99 percent effective at preventing pregnancy. They are documented to be safe for use in the adolescent population. However, the implant is currently used by less than 1% of U.S. women using contraception, and by 0.5% of those aged 15-19 years (13).

It is well documented that women using the contraceptive implant can expect changes in their menstrual bleeding patterns, and these changes account for the most commonly cited reason for method discontinuation. The bleeding pattern women experience in the first three months after insertion is predictive of future bleeding patterns throughout the duration of use (14). When analyzing 11 clinical trials, bleeding patterns were described as infrequent bleeding in 33.3% of 90-day cycles, amenorrhea in 21.4% of cycles, prolonged bleeding in 16.9% of cycles, and frequent bleeding in 6.1% of cycles (15).

There have been studies that propose management options for treating bothersome bleeding associated with the etonogestrel contraceptive implant – such options include combined oral contraceptive pills, non-steroidal anti-inflammatory agents, mefenamic acid, mifepristone, and doxycycline. Unfortunately there is limited clinical data supporting the effectiveness of these treatments (16-18). To our knowledge, there have been no studies investigating the use of oral progesterone for management of bothersome bleeding associated with the contraceptive implant. Given the success of norethindrone acetate in the management of pain and bleeding in adolescents with endometriosis (19), we chose to use norethindrone acetate as our oral progestin of choice for managing bothersome bleeding associated with the contraceptive implant.

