Prolonged bleeding	Any bleeding-spotting episode (uninterrupted) lasting more than 14 days in the 90-day reference period

Table I: WHO bleeding descriptions and patterns

Norethindrone acetate (aygestin) will be used to manage bothersome bleeding. Patients will be prescribed aygestin 5 mg by mouth twice daily for one month, followed by aygestin 5 mg by mouth once daily for two months. Medication will then be discontinued. Patients will be evaluated in the office three months after medication initiation, and then again six months after medication initiation. If the patient is unable to take norethindrone acetate (aygestin) due to medical contraindications or cost, they will receive medroxyprogesterone acetate (provera) 10 mg once daily as alternate oral progesterone. Figure 1 below highlights the study design.

[figure not shown]

Figure 1: Study design

During the aygestin administration, patients will again receive daily SMS texts in the evening via the Qualtrics SMS program asking them to respond with their bleeding pattern that day. We will record responses according to the World Health Organization definitions of bleeding: (a) bleeding day, (b) spotting day, (c) bleeding-free day. Patients not reporting bothersome bleeding after the initial 90 days will continue to record bleeding via SMS texts for the next 6 months to serve as the control group (normal bleeding group).

Participants will be compensated as an incentive to increase daily participation. The participant will receive a pre-paid card if they respond to >70% of text messages over each 90-day cycle and attend the scheduled office visit. Patients will receive a \$5 pre-paid card at visit one (3 months after insertion of etonorgestrel implant), \$10 pre-paid card at visit two (6 months after insertion of etonorgestrel implant), and a \$15 pre-paid card at visit three (9 months after insertion of etonogestrel implant).

At the completion of the study, 9 months after enrollment, participants will receive a SMS text message via Qualtrics with a link to a 12 question follow up survey. The post study questionnaire will assess overall satisfaction with the etonogestrel implant and evaluate participants' perceptions of text messaging as a tool to collect information. See Appendix II.

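### The days 1–90 diary forms the non-randomised groups and, as the SAP reads, is also the first repeated measure, so regression to the mean inflates the group-by-time test

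*SAP*

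**What the plan says.** **How groups are formed.** Protocol, Data Collection and Analysis: "On day 90, descriptive tallies of the responses will be done", and an algorithm applies the Table I definitions to the first 90 days of texts. "Participants who have at least a single episode of FB or PB will be assigned the label of" bothersome bleeding. FB means more than five bleeding-spotting episodes in the 90 days, and PB an episode longer than 14 days. Labelled participants are offered aygestin and stay in that group whatever they take: "data from those in the Bothersome Bleeding group will be assigned to the aygestin group, despite that they are not taking it". Under Materials and Methods, the others "will continue to record bleeding via SMS texts for the next 6 months to serve as the control group (normal bleeding group"). There is no randomisation, no separate qualifying window and no untreated comparator with bothersome bleeding.

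**How they are compared.** The SAP reports, for the primary hypothesis, "repeated measures ANOVA (RM-ANOVA) with two groups and three measurements (summary statistics at day-90, day-180, and day-270"). It gives no baseline adjustment, does not define the summary statistic and does not say which effect (group, time or group-by-time) is the test. It also removes participants who did not "respond at least 70% of the days during each 90-day time period".

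**The protocol differs.** Its Data Analysis section plans to "compare the first 30 day average bleeding value, the 90 day bleeding average, and the 180 day bleeding average between the two groups". The time origin is not stated, but these windows appear to start after classification.

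**The concern.** If day-90 means the summary of days 1–90, the same data select the groups and then serve as their starting value. A woman is labelled partly because of her stable bleeding tendency and partly because those 90 days happened to be bad. The second part does not carry forward. The labelled group therefore drifts towards better scores and the unlabelled group towards worse ones, with no drug effect at all. A group-by-time test reads this convergence as a treatment effect. An inert drug could then give a significant result on the primary hypothesis, in the favourable direction, and the analysis as written could not tell the two explanations apart.

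**Working it through.** **1. What day-90 covers (inference).** The SAP's minimum of 189 responses is 70% of the nine-month trial: 0.70 × 270 = 189. It also applies the 70% rule to each 90-day period. Three measurements at days 90, 180 and 270 then fit three consecutive windows: 1–90, 91–180 and 181–270.

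**2. Which effect is tested (inference).** Reproduce the SAP's sample size with f = 0.25, α = 0.05, k = 2 groups, m = 3 measurements and correlation ρ = 0.5 (assumed; the SAP gives none).

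- Interaction or time: λ = f²·N·m/(1−ρ), df = 2 and 2(N−2).
  - N = 28: λ = 0.0625×28×3/0.5 = 10.5, df 2 and 52, power 81%.
  - N = 39: λ = 14.625, df 2 and 74, power 92.9% (SAP: 93%).
- Between groups: λ = f²·N·m/[1+(m−1)ρ]. Power of 80% needs N = 86 (λ = 0.0625×86×3/2 = 8.06). At N = 39 power is 46%.

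The SAP's figures therefore fit an interaction or a time test equally well and rule out a between-group test. Of the two, only the interaction compares the arms.

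**3. Expected false shift.** With equal between-window correlation ρ and no drug effect, a first-window group difference Δ becomes ρΔ later, so the false differential change is (1−ρ)Δ. In a normal model with a 21/18 split on the score itself, the simulated change at ρ = 0.3 is 1.10 SD, so Δ = 1.10/0.7 = 1.57 SD. At ρ = 0.5 the formula gives 0.5×1.57 = 0.785 SD; simulation gives 0.78.

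**4. False-positive rate, normal model (N = 39, nominal 5%).** Columns give the assumed correlation of the grouping index with the first-window score.

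| ρ | 1.0 | 0.7 | 0.4 |
|---|---|---|---|
| 0.3 | 92% | 58% | 20% |
| 0.5 | 76% | 40% | 16% |
| 0.7 | 49% | 26% | 11% |
| 0.9 | 19% | 11% | 7% |

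**5. False-positive rate with the actual rule.** The label is an episode pattern, not the score, so it was modelled directly: a 270-day two-state daily diary, the Table I rule on days 1–90, the protocol's daily score (1 none, 0.5 spotting, 0 bleeding) averaged per window, and no drug effect. Three separately specified models:

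| Labelled share | Between-window correlation | Group-by-time rejects |
|---|---|---|
| 58% | 0.36 / 0.52 / 0.68 | 82% / 64% / 43% |
| 60–62% | 0.27 / 0.50 / 0.67 / 0.79 | 86% / 63% / 46% / 34% |
| 69% | 0.17 / 0.37 / 0.56 / 0.74 / 0.80 | 92% / 82% / 65% / 43% / 35% |

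The SAP's own share is 21/39 = 54%. A further model with 47–56% labelled and correlations 0.18–0.68 gave 40% to 94%. At correlations of 0.85–0.89 the rate falls to 20–25%. A Greenhouse-Geisser correction moves the rate by no more than about 2.5 points.

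In the 58% runs the false shift is 0.08 to 0.16 score points: 0.08×90 ≈ 7 and 0.16×90 ≈ 14 bleeding days per 90. The before/after test in the Intervention arm alone rejects in 20% to 44%. Virtually all group-by-time rejections point to benefit.

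**6. Is selection the cause?** Randomly permuting the labels returns the rate to about 5%.

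**7. The other possible effects.** A group main effect rejects in 97–100%, against the drug, because the groups differ by construction. A time effect rejects in about 5% but does not compare the arms.

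**8. Proposed analysis.** ANCOVA on the later windows, adjusting for the days 1–90 score, rejects in 4% to 7% in the main null runs.

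**The case against.** - **The SAP does not name group-by-time.** True, and the power figures cannot separate it from a time test. The point is conditional on that reading. The alternatives do not rescue the plan (step 7).
- **The 0–1 score is imported.** The SAP says only summary statistics; the protocol defines the score for a plotted curve. The shift in score points and bleeding days depends on this. Another bleeding summary of days 1–90 would probably be affected too, by an unknown amount.
- **The protocol's windows largely avoid the problem.** If the 30-, 90- and 180-day averages start after day 90, the null rejection rate is 6.5% to 9.7%. But the SAP is later, specific, and describes what was done.
- **The correlations are assumed.** This stands. The Background section says early bleeding predicts later bleeding, which favours the lower end of the range. Predictive is not perfectly stable, and 20–25% at 0.85–0.89 is still far above 5%.
- **Calibration to published patterns.** The Background section reports "infrequent bleeding in 33.3% of 90-day cycles, amenorrhea in 21.4% of cycles". Fitting roughly to those shares gives 94%, 83% and 60% at correlations 0.33, 0.50 and 0.67. That fit has 11% frequent and 17% prolonged bleeding, so at most 28% labelled against 54% here. These figures carry less weight than the 58% runs.
- **The ANCOVA is not guaranteed.** The label is a pattern and the covariate a mean, so the pattern may predict later bleeding beyond the mean. One of eleven further settings reached 9%, nearly all towards benefit. The protocol also speaks of what patients report at the three-month visit, so assignment may not be purely algorithmic. In a stress run where the label was an equal mix of the first window and stable tendency (normal windows, correlation 0.5), ANCOVA rejected in 50%, against the drug. These limits belong in the report; they do not defend the three-point test.

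**Conclusion.** The concern holds. On the natural reading of the SAP, the window that defines the groups is also their starting measure. If group-by-time is the primary test, its false-positive rate is roughly 40% to 80% at moderate between-window correlations and still 20–25% at very high ones, with the error almost always favouring the drug.

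This rests on four assumptions: day-90 summarises days 1–90; the interaction is the tested effect; the summary behaves like the protocol's daily score; and bleeding is neither perfectly stable between windows nor unrelated to the label. The simulations also assume complete diaries and no time trend. Confidence in the mechanism and direction is high; the exact rate is not known. Because this is the analysis of the primary hypothesis, it must be corrected before any efficacy statement.

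**What to change.** 1. Name the tested effect and define the summary statistic.
2. Remove days 1–90 from the outcome measures and use that score as a baseline covariate: ANCOVA, or a repeated-measures model, on the days 91–180 and 181–270 summaries. Dropping day-90 without adjusting is not enough for a group comparison: the unadjusted later-window difference rejected in 45–100% of null runs when groups were split on the score.
3. Report the three-point group-by-time test and the Intervention arm's before/after change as descriptive only.
4. The days 91–180 versus 181–270 contrast may be supportive. It tests withdrawal. It holds its level under constant correlation (3.9–5.6%), but if correlation decays it is biased against benefit (6–13% with the Table I label, 14–26% if the label is the score).
5. Reconcile the SAP time points with the 30-, 90- and 180-day averages in the protocol's Data Analysis section.
6. State that the re-analysis is post hoc, that baseline adjustment does not remove confounding from non-random assignment, and that efficacy is therefore not established. Say how the label was assigned in practice, since the adjustment can be biased against the drug if assignment also reflected stable bleeding tendency.

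**Cost.** SAP wording and one re-run on data already collected. Group and covariate are strongly correlated (about 0.6 to 0.8), so power falls: at 18 vs 21, 80% power needs about 0.08 to 0.18 score points (0.08×90 ≈ 7 to 0.18×90 ≈ 16 bleeding days per 90). The resulting claim will be less favourable.
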